9.3.3 Covariates

The covariates listed below consist of demographics, medications, comorbidities, and other variables that are hypothesized to confound the relationship between exposure and outcome. Covariates will be identified based on data recorded within 180 days prior to or on the index date (date of

dispensing/initiation of the exposure), unless otherwise specified. If multiple measurements are made in the baseline period, then the most recent measurement will be used.

There is an additional variable for “doubt diagnosis” related to each disease diagnosis. Only confirmed diagnoses will be used for all disease variables (this represents ~95% of all diagnoses).

Absolute and relative frequencies of each covariate will also be reported. Detailed descriptions of the listed covariates can be found in Annexes 2 and 3. The measure definitions for diagnoses are subject to modification to further incorporate disease codes/names as deemed appropriate upon further exploration of the data during study implementation.

Demographics (last recorded)

- Age
- Sex
- Year of Cohort Entry
- Hospital Size (as a proxy for urban/rural).

Concomitant Medications

- Oral/Injected Corticosteroids
- Short acting beta agonist (SABA) (number of claims)
- Short acting muscarinic antagonist (SAMA) (number of claims)
- Systemic Xanthines
- Systemic Antileukotrienes
- Interleukin Inhibitors for Asthma
- Non-steroidal Respiratory Anti-inflammatories
- Opioids/Narcotics
- Systemic Antihistamines
- Oral Antibiotics for a Respiratory Condition (number of claims)
- Cough and Cold Preparations
- Diabetes Mellitus Medications, excluding Insulin
- Insulin
- Cytostatics
- Antirheumatics, Biologic
- Antirheumatics, Non-Steroidal
- Antithrombotic Agents
- Lipid-lowering Agents
- Antihypertensives/Diuretics
- Antiepileptics/Psycholeptics/Psychoanaleptics
- Antipsoriatics
- Antivirals
- Thyroid Therapies
- Vaccinations

[Antibiotics + Respiratory diagnosis, [REDACTED] can try to find antibiotics specific to respiratory conditions]

Comorbidities/Symptoms

- COPD Exacerbations (number of exacerbations)
- All-Cause Hospitalization
- Hospitalization due to Respiratory Condition
- Acute Myocardial Infarction, AMI
- Angina Pectoris
- Peripheral Vascular Disease, PVD
- Heart Failure, HF

- Hypertension
- Cardiac Arrhythmias
- Cerebrovascular Disease
- Any Cancer (except nonmelanoma skin cancer)
- Allergic Rhinitis
- Chronic Sinusitis
- Bronchiectasis
- Pneumonia
- Chronic Bronchitis
- Tuberculosis
- Influenza
- Anxiety
- Dementia
- Depression
- Osteoporosis
- Acute Liver Injury or Failure
- Chronic Kidney Disease, CKD
- Peptic Ulcer Disease, PUD
- Gastroesophageal Reflux Disease, GERD
- Type 1 Diabetes Mellitus
- Type 2 Diabetes Mellitus
- Hypothyroidism
- Hyperthyroidism
- Anemia
- Rheumatoid Arthritis
- Lupus
- Inflammatory Bowel Disease, IBD
- Multiple Sclerosis, MS
- Psoriasis and Psoriatic Arthritis
- Eczema
- Blood eosinophil concentration (will be reported in the descriptive summary, but not included in the propensity score model given that this lab value is available for <10% of COPD patients in this data source).

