8. RESEARCH QUESTION AND OBJECTIVES

To compare the early intervention effectiveness of Tio/Olo vs. Tio among COPD patients.

The primary objective of this study is to:

- Compare time to LAMA/LABA/ICS triple therapy initiation among initiators of Tio/Olo vs. initiators of Tio.

The secondary objectives of the study are to compare the following among initiators of Tio/Olo vs. initiators of Tio:

Secondary outcomes

- Time to First Moderate or Severe COPD Exacerbation
 - Time to First Moderate COPD Exacerbation
 - Time to First Severe COPD Exacerbation
- Number of Moderate or Severe COPD Exacerbations
 - Number of Moderate COPD Exacerbations
 - Number of Severe COPD Exacerbations

Further endpoints:

- All-Cause Mortality,
- Number of Unique Pulmonary Medication Prescriptions
- Number of Hospitalizations for a Respiratory Condition
- Major Cardiovascular Adverse Events (MACE)
- Home oxygen therapy (HOT)

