9.2.2 Study population

The study cohort will include all patients who initiate Tiotropium/Olodaterol (Tio/Olo) or Tiotropium (Tio) during the patient selection period. Initiation (new use) will be determined based on no prescription claims for Tio/Olo or Tio during the baseline period or during all available data prior to cohort entry date. All patients will additionally be required to have a second claim for the index medication within 60 days after cohort entry to ensure primary adherence of index therapy.

The following exclusion criteria will then be applied to generate the unmatched cohort:

- Aged <40 years on cohort entry.

[figure not shown]
Proprietary confidential information © 2020 Boehringer Ingelheim International GmbH or one or more of its affiliated companies

- Any LAMA, LABA, ICS maintenance therapy (alone or in combination) during the 180-day baseline period prior to cohort entry for maintenance treatment and not cough, i.e. duration >30 days, or any prescription within the 30 days prior to cohort entry.
- Patients without continuous enrolment (days since first inpatient/outpatient encounter in the data) during the baseline period.
- No prior diagnosis of COPD [ICD-10: J41*, J43*, J44* and doubt (UTAGAIFLG) = 0 (no)]
- Patients without a second prescription claim of their index medication within 60 days after the cohort entry date.
- Diagnosis of asthma [ICD-10: J45* and doubt (UTAGAIFLG) = 0 (no)] during the baseline period.
- Diagnosis of lung cancer [ICD-10: C34*, D02.2, Z80.1, Z85.1 and doubt (UTALAIFLG) = 0 (no)] or lung transplant (Health claim code: 150317670, 150322510, 150322610, 150336510, 150336610, 150336710, 150399270) prior to the cohort entry date using all available data.
- Patients who initiate both Tio/Olo and Tio simultaneously on the cohort entry date.
- Any use of triple therapy (LAMA + LABA + ICS) during the baseline period or between the cohort entry date and 1 day prior to the start of follow-up.

All patients will be selected into the first treatment arm (Tio/Olo or Tio) that they qualify for and will not be allowed to re-enter the cohort by design.

The cohort will then be used to construct two matched cohorts (not mutually exclusive) according to the: 1) basic propensity scores and 2) high dimensional propensity scores

Figure 2 Depicts the flow diagram of patients.

Basic Propensity Score Matching

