9.4 DATA SOURCES

The proposed study will utilize data from Medical Data Vision (MDV).

MDV is an electronic, record-based healthcare database that spans from April 1, 2008 to 31 March 2019, and contains 25.1 million observable patients. It contains patient-level information on demographics, diagnoses and prescription information from 374 medical facilities across Japan. The distribution of patients in the database is similar to that of the national demographics for patients seeking healthcare, although the MDV database has more elderly and sicker patients.

The Japanese health care structure enables anyone to seek medical treatment at any facility of their choosing, including hospitals. Thus, acute hospitals in Japan consist of both primary (outpatient) and secondary (inpatient) care facilities. In fact, the MDV database is built out of more than 80% outpatient data, which allows for identification of patients who visit hospitals without severe conditions. These hospitals follow a diagnosis procedure combination (DPC) billing structure unique to Japan that enables capture of inpatient discharge summary

information (disease name, operations, adjuvant treatment, etc.), health claims for procedures (surgery information, departments, wards, etc.), and health claims for treatments (medications, medical devices, devices, etc.). A smaller subset of consenting hospitals also provide data on blood test results.

Thus, it is expected that 1) patients with COPD in these hospitals provide a good representation of the general Japanese COPD population; and 2) data from patients treated in the different hospitals cannot be linked. Due to the nature of the database, inclusion criteria to ensure that the patients are treated for COPD in the same hospitals continuously are defined as described in [Section 9.2.2](#).

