Additionally, the MDV database also poses some limitations inherent to prescription claims data. Electronic outpatient pharmacy dispensing records are considered accurate because pharmacists fill prescriptions with little room for interpretation and are reimbursed by the government on the basis of detailed, complete, and accurate claims submitted electronically (Sternbach 1988, Levy 2003). Pharmacy dispensing information is usually seen as the gold standard of drug exposure information compared to self-reported information (West 1995) or prescribing records in outpatient medical records (West 1994). However, claims data are subject to certain limitations. The presence of a claim for a filled prescription does not indicate that the medication was consumed or that it was taken as prescribed, and any medications filled over-the-counter or provided as samples by the physician will not be observed in the claims data. This concern is somewhat mitigated by requiring 2 claims within 60 days for cohort entry. Finally, patients are required not to have a claim for Tiotropium/Olodaterol or Tiotropium during the baseline period, but patients may have taken maintenance therapies prior to the start of the baseline period.

MDV database only captures in-patient deaths, and mortality, one of the secondary outcomes, maybe under-reported in the data. However, the magnitude of the underestimation is unlikely to differ by exposure and comparison cohorts.

In the analytical portion of this protocol, propensity score matching will be used to ultimately derive the causal parameters of interest. Many covariates are included in the prediction model of the propensity scores, but as with all non-interventional studies, the potential for unmeasured and residual confounding cannot be ruled out.

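### Time since first recorded COPD diagnosis is in neither the entry rules nor the propensity scores, so residual confounding by disease duration is plausible and would go unseen; it can be partly measured from data already held

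*Combined protocol and SAP*

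**What the plan says.** The research question in section 8 is "To compare the early intervention effectiveness of Tio/Olo vs. Tio among COPD patients". The documents do not define early.

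Three rules in section 9.2.2 bear on it:

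- Patients without a prior confirmed COPD code (J41, J43 or J44 families) are excluded. There is no upper limit on how long ago the first code was recorded.
- New use means "no prescription claims for Tio/Olo or Tio during the baseline period or during all available data prior to cohort entry date".
- Other maintenance treatment is checked over a shorter window. The exclusion begins "Any LAMA, LABA, ICS maintenance therapy (alone or in combination) during the 180-day baseline period prior to cohort entry", and section 9.9 acknowledges that "patients may have taken maintenance therapies prior to the start of the baseline period".

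On covariates, section 9.3.3 says: "Covariates will be identified based on data recorded within 180 days prior to or on the index date". The basic score uses age, sex, calendar year, hospital size and the section 9.3.3 list. The hdPS adds empirically ranked codes and service-intensity quartiles.

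Section 9.12 accepts that the two groups of initiators may differ in clinical course and severity, and relies on matching to deal with this.

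**The concern.** Duration of disease could plausibly affect both the choice of initial treatment and the chance of later escalation. Section 7 places the combination after monotherapy in patients who remain symptomatic, and treats escalation to triple therapy as a proxy for worsening disease. If patients with longer-standing COPD are more often started on one of the two products and also escalate sooner or later than others, the hazard ratio absorbs part of that difference.

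Matching balances duration only so far as the variables in the score happen to track it. Section 9.7.1.1 reports standardized differences for the section 9.3.3 variables, so an imbalance in duration would not appear in the balance tables. The primary hazard ratio could then carry a moderate bias that nothing in the planned output would reveal.

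**Working it through.** **1. Text check: where could duration enter?**

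- Entry rules (9.2.2): any prior confirmed COPD code is enough. The new-user rule and the 180-day washout describe treatment stage, not time since diagnosis. The patient counts in section 9.5 refer to a COPD diagnosis in the baseline period, but that does not limit the age of the first code either.
- Prespecified covariates (9.3.3): no time since first COPD code, no spirometry and no GOLD stage. The indirect markers are age, exacerbation count, all-cause and respiratory hospitalisation, SABA and SAMA claims, xanthines and chronic bronchitis.
- hdPS additions (9.2.2): codes ranked on prevalence, recurrence and association with exposure and outcome, plus quartiles of total and distinct codes. None of these is a time since diagnosis.
- Subgroups (9.7.2): not applicable. Sensitivity analyses (9.7.3): none of the five concerns duration or a longer look-back.

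**2. Can it be derived?** Section 9.4 says that the database "spans from April 1, 2008 to 31 March 2019". From 1 April 2008 to the first possible entry date (28 September 2015) is 7.5 years, and to the last (31 December 2018) 10.7 years. These are maxima: a patient's own history starts at the first encounter, and section 9.2.1 requires only 180 days. Section 9.2.2 already searches all available data for earlier Tio or Tio/Olo, lung cancer and lung transplant.

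**3. Reference value from the plan.** Section 9.5 assumes one-year escalation of 6% (Tio/Olo) and 10% (Tio). The implied hazard ratio is ln(0.90)/ln(0.94) = 1.703 for Tio vs Tio/Olo, or 1/1.703 = 0.587 for Tio/Olo vs Tio. The plan prints 1.73 in section 9.5 and 1.7 in the abstract. By the Schoenfeld formula (1:1, two-sided 0.05, 90% power), 1.73 gives 140 events (stated: 141). The value 1.703 gives 148.4 events, and 148.4/0.08 = about 1,854 patients (stated: 1,856). The planned size is therefore reproduced within rounding and does not bear on this point. Only 0.587 is used below.

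**4. Possible size of the bias (assumed inputs, not in the documents).** Let g be the hazard ratio for escalation in long-standing versus recent COPD, and p1 and p0 the prevalence of long-standing COPD in matched Tio/Olo and Tio patients. The observed HR is multiplied by about

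B = [1 + p1(g − 1)] / [1 + p0(g − 1)].

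| g | p1 50%, p0 40% | p1 60%, p0 40% | p1 40%, p0 50% | p1 40%, p0 60% |
|---|---|---|---|---|
| 1.5 | 1.042 | 1.083 | 0.960 | 0.923 |
| 2 | 1.071 | 1.143 | 0.933 | 0.875 |
| 3 | 1.111 | 1.222 | 0.900 | 0.818 |

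For example, g = 3 with 60% vs 40% gives (1 + 0.6 × 2)/(1 + 0.4 × 2) = 2.2/1.8 = 1.222.

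Applied to 0.587, the extremes are 0.587 × 1.042 = 0.61 and 0.587 × 1.222 = 0.72 in one direction, and 0.587 × 0.960 = 0.56 and 0.587 × 0.818 = 0.48 in the other. The table takes the imbalance as it stands after matching. If the proxies removed part of it, B would be closer to 1.

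**The case against.** **Early may mean treatment stage.** The plan speaks of patients newly initiating therapy, requires no earlier Tio or Tio/Olo, and applies a 180-day washout for other maintenance drugs. This is a fair reading, and it stands. A reader might infer that the early-intervention conclusion fails because disease duration is not restricted. The documents do not support that, because they never say that early refers to the disease. What is missing is a sentence that says which sense is meant. Even the treatment sense is only partly secured, given the limitation admitted in section 9.9.

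**Duration is not wholly uncontrolled.** This also stands. The listed covariates and the hdPS codes will carry some of the information, and the 180-day rule allows for exceptions. Annexes 2 and 3 are not among the documents, but section 9.3.3 says that they describe the listed covariates, and time since first code is not listed. The accurate statement is that duration is neither measured nor directly adjusted for.

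**First recorded code is a weak measure.** Section 9.4 says that data from different hospitals cannot be linked, so a patient with long-standing COPD who changed hospital recently looks newly diagnosed. Section 9.7.3 adds that the J41 code is often used in patients without chronic bronchitis. Adding look-back length does not recover the lost history; it only helps to compare patients with similar observable time. This limits what the adjustment can achieve, but is no reason to leave out a variable that can be had at little cost.

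**A subset of recently coded patients should not carry the conclusion.** It would still contain long-standing disease, and it may be small. If 60 to 65% of the 1,829 Tio/Olo users had a first code more than a year old (an assumption), 640 to 732 would remain, or at most 1,280 to 1,463 patients after 1:1 matching, against the planned 1,856. If the share were 40%, the ceiling would be 2 × 0.60 × 1,829 = 2,195. This objection stands in full.

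**Conclusion.** The point holds in a limited form. No entry rule and no prespecified score covariate directly measures time since first recorded COPD diagnosis, the available proxies are partial, and the planned balance tables would not show an imbalance. Because section 9.12 itself allows for differences in clinical course and severity, residual confounding by duration is plausible.

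It is not shown to be present. A reader might infer that the bias runs towards the null, so that the plan would merely be conservative. The documents give no basis for a direction. Section 7 speaks of symptoms, not years since diagnosis, and nothing reports duration by arm. Under the assumed inputs the HR could move by about 4 to 22% upwards or 4 to 18% downwards. Those figures assume a hazard ratio of 1.5 to 3 for long-standing disease and a post-matching imbalance of 10 to 20 points, neither of which has a source in the documents.

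The study can run without this change, but the change is cheap and would bring a plausible confounder into view.

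**What to change.** 1. From all available data, derive time since the first confirmed COPD code in the J41, J43 or J44 families (for example 0–3, 3–12 and over 12 months before entry) and the length of observable look-back. Where sensitivity analysis 3 drops J41, derive the time from J43 and J44 only.
2. Add both variables to the basic and the hdPS models, and report their standardized differences before and after matching.
3. State in section 9.9 that the measure is left-truncated, because hospitals cannot be linked and only 180 days of history are required. A patient with less than 12 months of look-back cannot fall in the longest category, which is why the two variables belong together.
4. In section 8, describe early intervention as initiation of maintenance therapy rather than as early disease.
5. Optionally, report the primary HR with its CI in patients first coded within 12 months, as a sensitivity analysis. The main conclusion stays with the full matched cohort.

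Cost: two derived covariates, possibly a few lost matches, and imperfect measurement of true duration. No new data are needed.

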9.4 DATA SOURCES

The proposed study will utilize data from Medical Data Vision (MDV).

MDV is an electronic, record-based healthcare database that spans from April 1, 2008 to 31 March 2019, and contains 25.1 million observable patients. It contains patient-level information on demographics, diagnoses and prescription information from 374 medical facilities across Japan. The distribution of patients in the database is similar to that of the national demographics for patients seeking healthcare, although the MDV database has more elderly and sicker patients.

The Japanese health care structure enables anyone to seek medical treatment at any facility of their choosing, including hospitals. Thus, acute hospitals in Japan consist of both primary (outpatient) and secondary (inpatient) care facilities. In fact, the MDV database is built out of more than 80% outpatient data, which allows for identification of patients who visit hospitals without severe conditions. These hospitals follow a diagnosis procedure combination (DPC) billing structure unique to Japan that enables capture of inpatient discharge summary

information (disease name, operations, adjuvant treatment, etc.), health claims for procedures (surgery information, departments, wards, etc.), and health claims for treatments (medications, medical devices, devices, etc.). A smaller subset of consenting hospitals also provide data on blood test results.

Thus, it is expected that 1) patients with COPD in these hospitals provide a good representation of the general Japanese COPD population; and 2) data from patients treated in the different hospitals cannot be linked. Due to the nature of the database, inclusion criteria to ensure that the patients are treated for COPD in the same hospitals continuously are defined as described in [Section 9.2.2](#).

9.5 STUDY SIZE

There are 1,829 new users of *Tiotropium/Olodaterol* and 13,132 new users of *Tiotropium* between 28 Sep 2015 and 31 October 2018 who satisfied the initial inclusion criteria of new use with at least 2 prescriptions for the index medication within 60 days, and excluding patients without a COPD diagnosis during the baseline period, age <40, diagnosis of asthma during the baseline period, no history of lung cancer or lung transplant, any LAMA, LABA, or ICS maintenance therapy within the 30 days prior to cohort entry, and without continuous enrolment (days since first inpatient/outpatient encounter in the data) during the baseline period.

Based on the result of study by Hahn B et al, it is assumed that the triple therapy initiation rate during 1 year is 6% in Tio+Olo group and 10% in Tio group. In total, 1856 patients are needed to observe 141 events and to detect the difference (HR of 1.73) with 2-sided alpha of 0.05 and 90% power.

After propensity score matching, it will be assessed whether sufficient number of sample size is available to detect the expected difference. If not available, the treatment difference will be explored in highly explorative manner (i.e., p-value is considered descriptively and point estimate with confidence interval is focused).

9.6 DATA MANAGEMENT

Dataset

The Medical Data Vision dataset is comprised of administrative records of longitudinal inpatient, outpatient and drug data from multiple hospitals that have been standardized and de-identified prior to use for the analysis. The statistical analysis will be conducted using the

COPD Maintenance Therapy Drug Duration

Given limited information on treatment duration in the MDV data, a days supply of 14 days will be assumed for “Spiolto Respimat 28puffs.” Otherwise, 30 days will be assumed for all LAMA, LABA, and ICS maintenance therapies, including “Spiriva Inhalation Capsules 18microg”, “Spiriva 2.5microg Respimat 60puffs 150microg”, “Spiriva 1.25microg Respimat 60puffs 75microg”, and “Spiolto Respimat 60puffs”. A grace period of 14 days between assumed end of days supply and subsequent prescription will be used as an allowable gap.

Handling of Missing Data

Missing data that occurs in covariates or descriptive variables will be classified as its own level (i.e. missing data indicator). In addition, a feasibility assessment before beginning the

analyses will be done, and variables with >75 % missing values will be excluded from all analyses, other than baseline characteristics. If a variable is left with only one level other than missing, the variable will be excluded completely from all analyses.

